8.1.1 Definition of variables

The main efficacy variable is defined as the following:

- **Maximum Increase from Baseline:** the Maximum Increase from Baseline (Day 1, predose) is defined as the highest positive change from Baseline during the study. In the event that the platelet count was to decrease during the study the Maximum Increase from Baseline may be negative and would correspond to the smallest decrease from the Baseline value

The following additional variables will be defined for the platelet count, the calculation rules for which are provided in the section immediately below:

- **Response:** a platelet count $\geq 30 \times 10^9/L$ and at least 2-fold increase from the Baseline value, by visit, and at any timepoint during the study
- **Time to Response:** the first time that a given response is achieved during the study. Thus, in the event that the platelet count was to increase above the threshold level, decrease below the threshold level, and subsequently increase again the time to response would be to the first time the definition of response was achieved. The time to response will be calculated in days and presented to 1 decimal place in the listings.

Time to response (days) = Date/time of first response – Date/time of first dose of UCB7665

- **‘No’ or ‘Loss of’ Response:** a platelet count $< 30 \times 10^9/L$ OR $\geq 30 \times 10^9/L$ WITHOUT at least a 2-fold increase from the Baseline value, by visit
- **Duration of Response (including Complete Response, Response and Platelet Count $\geq 50 \times 10^9/L$):** the duration of the first time the response was achieved to first loss of response. The duration of response will be calculated in days and presented to 1 decimal place in the listings.

Duration of response (days) = Date/time of loss of first response – Date/time of first response, where “loss of first response” is defined as platelet count $< 30 \times 10^9/L$ OR (platelet count $\geq 30 \times 10^9/L$ WITHOUT at least a 2-fold increase from the Baseline value)

If the platelet value meets the criterion for a specific response for a second time (following a loss of initial response), the second response period will be added to the overall duration of response. This rule will be applied for any subsequent ‘response periods’. For subject in whom the response is maintained until the end of the study the duration of response will be calculated using the date of the end of study visit as the ‘end of response date’. Any such cases will be flagged in the data listings

- **Complete Response:** a platelet count $\geq 100 \times 10^9/L$, by visit, and at any timepoint during the study
- **‘No’ or ‘Loss of’ Complete Response:** a platelet count $< 100 \times 10^9/L$, by visit.

- Time to Complete Response: the time from starting treatment (Day 1) to achievement of Complete Response
- Platelet Count $\geq 50 \times 10^9/L$, by visit, and at any timepoint during the study
- ‘No’ or ‘Loss of’ Platelet Count $\geq 50 \times 10^9/L$: a platelet count $< 50 \times 10^9/L$, by visit.
- Time to Platelet Count $\geq 50 \times 10^9/L$: the time to Platelet Count $\geq 50 \times 10^9/L$ is defined as the time from starting treatment (Day 1) to achievement of Platelet Count $\geq 50 \times 10^9/L$
- Maximum: the maximum value for platelet count over all visits in the study
- Value and change from Baseline in platelet count over time
- Baseline-corrected AUEC for platelet count calculated from Baseline to the end of study visit for each of the defined dose arms.

For all the above response variables the following rules will apply:

- Both scheduled and unscheduled measurements may be included in the calculation of a response, time to response or duration of response
- The Baseline-corrected AUEC will be calculated according to the following rules:
 - The AUEC will be calculated according to the linear trapezoidal rule using protocol scheduled visits
 - Unscheduled visits will not be included in the calculation
 - No imputation of any missing data will be performed
 - To account for differences in the timing of Baseline samples for each subject the Baseline measurement will be considered as time zero in the calculation
 - The units of the AUEC will be $10^9/L \cdot \text{day}$
 - The measurements at Baseline and at the last visit must be available
 - A minimum of 10 out of 14 measurements must be available for the calculation in Dose Arm 1; a minimum of 9 out of 12 measurements must be available for the calculation in Dose Arm 2; a minimum of 8 out of 11 must be available for the calculation in Dose Arm 3; a minimum of 7 out of 9 must be available for the calculation in Dose Arms 4 and 5. These include the Baseline and measurement at the last visit
 - The AUEC will not be calculated in the case of early withdrawal from the study

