2.2.2 Efficacy variables

The efficacy variables are as follows where all variables relating to platelets refer to those measured by ACM Global Central Laboratory:

- Response during the study: platelet count $\geq 30 \times 10^9/L$ and at least 2-fold increase from the Baseline count
- Complete Response during the study: platelet count $\geq 100 \times 10^9/L$
- Platelet count $\geq 50 \times 10^9/L$ during the study
- Response by visit
- Complete Response by visit
- Platelet count $\geq 50 \times 10^9/L$ by visit

- The maximum value and maximum increase from Baseline in platelet count during the study
- Value and change from Baseline in platelet count over time
- Baseline-corrected area under the effect curve (AUEC) for platelet count calculated from Baseline to the end of study visit (Day 85 in the Observation Period in Dose Arm 1, Day 71 in the Observation Period in Dose Arm 2, Day 64 in the Observation Period in Dose Arm 3 and Day 57 in Observation Period in Dose Arms 4 and 5)
- Time to Response: time from starting treatment to achievement of Response
- Time to Complete Response: time from starting treatment to achievement of Complete Response
- Time to achieving platelet count $\geq 50 \times 10^9/L$
- Duration of Response: measured from achievement of Response to loss of Response (loss of Response defined as platelet count $< 30 \times 10^9/L$ or less than 2-fold increase of Baseline platelet count)
- Duration of Complete Response: measured from achievement of Complete Response to loss of Complete Response (loss of Complete Response defined as platelet count $< 100 \times 10^9/L$)
- Duration of platelet count $\geq 50 \times 10^9/L$: measured from achievement of platelet count $\geq 50 \times 10^9/L$ to reduction of platelet count $< 50 \times 10^9/L$
- Clinical Response: confirmation of platelet count $\geq 30 \times 10^9/L$ and at least 2-fold increase from the Baseline value and absence of bleeding
- Time to Clinical Response: time from starting treatment to achievement of Clinical Response
- Duration of Clinical Response: measured from achievement of Clinical Response to loss of Clinical Response (loss of Clinical Response defined as platelet count $< 30 \times 10^9/L$ or less than 2-fold increase from Baseline platelet count or presence of bleeding)
- Complete Clinical Response: confirmation of platelet count $\geq 100 \times 10^9/L$ and absence of bleeding

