3 DATA ANALYSIS CONSIDERATIONS

3.1 General presentation of summaries and analyses

Statistical evaluation will be performed by PAREXEL. The datasets will follow the UCB analysis data model (ADaM) specifications.

All analyses will be performed using SAS version 9.3 or higher (SAS Institute, Cary, North Carolina, United States of America). Continuous variables will be summarized by visit (where applicable) including number of subjects (n), arithmetic mean, SD, median, minimum and maximum. Categorical variables will be summarized by visit (where applicable) with frequency counts and percentages with 95% confidence intervals (CI) where stated. Geometric coefficient of variation (geoCV), geometric mean (geoMean) and 95% CI for the geoMean will also be presented in the descriptive statistics for the PK concentration data.

When reporting relative frequencies or other percentage values, the following rules apply:

- For values where all subjects fulfill certain criteria, the percentage value will be displayed as 100
- For values where the absolute frequency is zero, there will be no percentage displayed at all
- All other percentage displays will use 1 decimal place

Percentages displayed based on continuous data (eg, percentage changes from baseline) will be displayed to 1 decimal place.

When reporting descriptive statistics, the following rules will apply in general:

- n will be an integer
- Mean (arithmetic and geometric), SD and median will use 1 decimal place more than the original data
- Minimum and maximum will be reported using the same number of decimal places as the original value
- If no subjects have data at a given timepoint, for example, then only n=0 will be presented. If n<3, present the n, minimum and maximum only. If n=3, present the n, mean, median, minimum and maximum only. The other descriptive statistics will be left blank.

When reporting descriptive statistics for PK data, the following rules will apply with regard to rounding and precision:

- Individual values for PK concentration data will be reported to the same level of precision as received from the bioanalytical laboratory
- Descriptive statistics for PK concentration data will be reported to the same level of precision as the individual data for the minimum and maximum, and to 1 additional significant figure for the mean (arithmetic and geometric), median, SD and 95% CI for the geoMean
- Geometric CV will be reported as a percentage to 1 decimal place

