8.1.2 Presentation of results

The individual platelet measurements will be listed by dose arm and visit including changes from Baseline (Day 1, pre-dose). Descriptive summaries (including n, arithmetic mean, median, SD, minimum and maximum) will be presented by dose arm and scheduled visit for both absolute values and changes from Baseline based on the FAS only. Summary tabulations by dose arm will be repeated for the subgroups defined in [Section 4.8](#) (based on the FAS only too).

In addition, a separate listing and summary will be presented (by visit, where applicable) including the following:

- *Response by visit and over all visits
- Time to Response
- Duration of Response
- *Complete Response by visit and over all visits
- Time to Complete Response
- Duration of Complete Response
- *Platelet Count $\geq 50 \times 10^9/L$ by visit and over all visits
- Time to Platelet Count $\geq 50 \times 10^9/L$
- Duration of Platelet Count $\geq 50 \times 10^9/L$
- Maximum value
- Maximum Increase from Baseline
- Baseline-corrected AUEC

*All the above variables will be included in the listing. The number and percentage of responders (for variables denoted with an asterisk) will be tabulated separately as described in [Section 8.1.3.3](#).

Summary tabulations by dose arm will be repeated for the subgroups defined in [Section 4.8](#) (based on the FAS only).

Mean and mean change from Baseline platelet values will be plotted versus scheduled visit by dose arm with all dose arms overlaid on the same plot. Similar plots will be provided for response rate over time (response, complete response and platelet count $\geq 50 \times 10^9/L$). Mean median, mean change and median change from Baseline total IgG results will be plotted over time by dose arm with all dose arms overlaid on the same plot.

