8.1.3.2 Analysis of time to response

The time to first response will be analyzed with the log-rank test and displayed using Kaplan-Meier curves.

Kaplan-Meier curves will be presented for the variables Time to Response, Time to Complete Response, and Time to Platelet Count $\geq 50 \times 10^9/L$. Descriptive statistics will include the p-value for the log-rank test for the equality over dose arms. The point estimate for the median number of days to response with 90% CIs will be given if estimable. Further a summary including the number and percent of censored subjects, the number of responders and total subjects by dose arm and in total will be given.

For the purpose of the analysis subjects with no response will be censored at the end of the study or at the date of withdrawal.

Analyses will be performed for the FAS and repeated for the PPS.

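### Duration of response mixes two definitions and closes ongoing responses at the end-of-study visit, so its mean, SD and maximum can be understated, more so in arms with shorter follow-up

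*SAP*

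**What the plan says.** Section 8.1.1 describes duration of response as "the duration of the first time the response was achieved to first loss of response". The paragraph after the formula changes this. If a subject responds again after a loss, "the second response period will be added to the overall duration of response", and the same holds for any further periods.

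For a response that lasts to the end of the study, "the duration of response will be calculated using the date of the end of study visit as the" closing date. The only marker is in the listings: "Any such cases will be flagged in the data listings".

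Section 8.1.2 says that "a separate listing and summary will be presented (by visit, where applicable) including the following", and the list covers the durations of Response, Complete Response and platelet count of at least 50 × 10⁹/L. No special statistic is named for them, so the default in section 3.1 applies: "Continuous variables will be summarized by visit (where applicable) including number of subjects (n), arithmetic mean, SD, median, minimum and maximum". Section 8.2.1.1 refers back to the same rule for the two Clinical Response durations.

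Section 8.1.3.2 handles the front end of the same endpoint differently. Kaplan-Meier is used for the time-to variables, and "subjects with no response will be censored at the end of the study or at the date of withdrawal". No duration variable is included there.

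The end-of-study visit differs by arm. Section 2.2.2 places it at Day 85 in Dose Arm 1, Day 71 in Dose Arm 2, and "Day 64 in the Observation Period in Dose Arm 3 and Day 57 in Observation Period in Dose Arms 4 and 5".

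**The concern.** Under the definition of first response to first loss, a response still present at the last visit has an unknown end. Its observed length is a lower bound. The SAP averages that bound with completed durations as if the response had ended that day, and nothing in the summary table tells the reader how many values are of this kind. Elsewhere the SAP recognises the problem: time to response is censored, and Table 4-1 reports the duration of an ongoing adverse event with a greater-than sign.

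The last visit falls at a different time in each arm, so the ceiling on duration is not the same across arms. Summaries are given by dose arm and will be read side by side. The single-dose arms could look less durable than the five-dose arm because they are followed for less time after a given onset day.

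There is also a gap. The closing rule covers only responses kept to the end of the study. No end date is stated for a subject who withdraws while responding, or whose platelet data are cut at the start of rescue medication.

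**Working it through.** **Inputs from the SAP.** Weekly dosing with 5, 3, 2, 1 and 1 doses in Dose Arms 1 to 5 (section 2.3), an Observation Period of 8 weeks (section 3.2.1.2), and the end-of-study days in section 2.2.2.

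**Reproducing the end-of-study days.** Last dose day + 56:
- Arm 1: 29 + 56 = 85
- Arm 2: 15 + 56 = 71
- Arm 3: 8 + 56 = 64
- Arms 4 and 5: 1 + 56 = 57

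All agree with section 2.2.2. Follow-up from the first dose is therefore 84, 70, 63 and 56 days. For the same onset day, the ceiling on duration is 28 days lower in Arms 4 and 5 than in Arm 1.

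**Assumptions not in the SAP.** First response on Day 8 in every arm, one response period per subject, exponential time to loss, and the same true mean μ in every arm.

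**Formula.** With ceiling C = end-of-study day − 8, the expected summarised mean is μ × (1 − exp(−C/μ)), and the fraction still responding at the last visit is exp(−C/μ). The ceilings are 77, 63, 56 and 49 days.

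Example for μ = 30:
- Arm 1: 30 × (1 − exp(−77/30)) = 27.7
- Arms 4 and 5: 30 × (1 − exp(−49/30)) = 24.1

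| True mean (days) | Arm 1 | Arm 2 | Arm 3 | Arms 4 and 5 | Ongoing, Arm 1 to Arms 4 and 5 |
|---|---|---|---|---|---|
| 14 | 13.9 | 13.8 | 13.7 | 13.6 | 0% to 3% |
| 30 | 27.7 | 26.3 | 25.4 | 24.1 | 8% to 20% |
| 60 | 43.4 | 39.0 | 36.4 | 33.5 | 28% to 44% |

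The gap between Arm 1 and Arms 4 and 5, with no true difference, is 27.7 − 24.1 = 3.6 days at a true mean of 30 and 43.4 − 33.5 = 9.9 days at 60. At 14 days the largest shortfall is 3%.

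**Median.** The exponential median is μ × ln 2: 9.7, 20.8 and 41.6 days for the three rows. All lie below the shortest ceiling of 49 days, so the median is unchanged in every row. It moves only with longer responses: at a true mean of 90 days the median is 62.4, but Arm 3 (54% ongoing) would show 56 and Arms 4 and 5 (58% ongoing) would show 49.

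**The case against.** The strongest reply is that the derived variable is not first response to first loss. Once later periods are added, it is largely total time in response within the study. For a subject who completes, that quantity is fully observed, and closing the last period at the final visit is natural. This stands as far as it goes: under that reading censoring is not the issue. Two problems remain. The definition and the adding rule in section 8.1.1 describe different variables, and total time is still not comparable across windows of 56 to 84 days.

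A reader might infer that every duration summary is certainly biased low, or that arms could differ by four weeks with the same effect. The documents do not support that. They give no onset day and no expected duration. The bias is negligible for short responses, and the 28-day gap arises only for responses with the same onset day that last to the final visit in both arms. Nor is the median distorted in the scenarios tabulated above.

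Follow-up after the last dose is 56 days in every arm. If onset tracked the last dose, the ceilings would coincide. The arm difference arises because duration runs from onset.

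Finally, no test rests on duration. The log-rank test concerns time to response, the primary objective is safety, and the individual platelet plots and the listing flag show who is still responding. This limits the consequence but does not repair the summary table. Rescue is partly handled, since platelet data stop at its start; only the resulting end date is missing.

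**Conclusion.** The point holds conditionally. Section 8.1.1 gives two incompatible meanings to one variable. Under the first-response meaning, the closing rule understates the mean, SD and maximum whenever responses are ongoing at the last visit, and does so more in arms with shorter follow-up. The median is affected only when about half or more of an arm's responders are ongoing.

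The size depends on assumptions about onset and duration that the SAP does not supply. With onset on Day 8 and exponential loss, the spurious gap between Arm 1 and Arms 4 and 5 is 3.6 days at a true mean of 30, 9.9 days at 60, and negligible at 14. The endpoint is descriptive, so this is a correction the sponsor should make; it does not threaten the trial's main conclusions.

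**What to change.** In sections 8.1.1 and 8.1.2:

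1. Define duration of the first response as time from first response to first loss. Estimate it by Kaplan-Meier per arm, with ongoing responses censored at the last platelet count before end of study, withdrawal or rescue. Give the median with 90% CI where estimable, as in section 8.1.3.2.
2. Show the number of responses ongoing per arm in the summary table, not only in the listing.
3. If total time in response is kept, name it as a separate variable and report it over a common window in all arms, for example to Day 57. Do not scale it to a percentage of observed days, which creates the opposite artefact: at a true mean of 30 days, 27.7/84 = 33% in Arm 1 against 24.1/56 = 43% in Arms 4 and 5.
4. Carry the same wording into the Clinical Response durations in section 8.2.1.1.

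The cost is SAP wording and a few Kaplan-Meier tables from data already derived. The drawback is that medians may not be estimable in arms of 6 to 12 subjects, where only responders contribute. The count of ongoing responses would then carry the information.

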3.2.1.2 Study periods

For each subject the duration of the study is approximately 16 weeks.

- Screening Period: 1 to 28 days
- Dosing Period: 1 to 4 weeks; during the Dosing Period subjects will receive weekly doses of UCB7665 (5 doses of 4mg/kg [QWK] in Dose Arm 1, 3 doses of 7mg/kg [QWK] in Dose Arm 2, 2 doses of 10mg/kg [QWK] in Dose Arm 3, 1 dose of 15mg/kg in Dose Arm 4 and 1 dose of 20mg/kg in Dose Arm 5). The dose regimen may be adapted following review by the DMC
- Observation Period: 8 weeks; a visit will be scheduled 3 days after the final dose (or only dose administration for Dose Arms 4 and 5) and weekly thereafter to collect safety and efficacy data

The end of the study is defined as the date of the last visit of the last subject in the study.

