10.2 Adverse events

Adverse events will be recorded from the time of informed consent until study completion. All AEs will be coded ([Section 3.8](#)) and will be categorized by relationship to UCB7665.

In addition, AEs will be classified according to the CTCAE Version 4.03 for severity. For any AEs where it is not possible to provide a CTCAE grading, the events will be assessed using a standard intensity classification (mild, moderate and severe). For the purpose of the tabulations all CTCAE severity classifications will be mapped to a mild/moderate/severe grade as described in the below sections. Bleeding events classified as Grade 1 or Grade 2 (based on CTCAE) will not be reported as AEs as these will be assessed and reported as part of the ITP-BAT assessments. Bleeding events classified as Grade 3 or higher, based on CTCAE, will be reported as AEs.

A TEAE is defined as any event that was not present prior the first administration of UCB7665 or any unresolved event already present before the first administration of UCB7665 that worsens in intensity following exposure to treatment. Adverse events starting before the first administration of UCB7665 or after 8 weeks following the final dose of UCB7665 will not be considered as TEAEs. Such events will be listed only.

Where dates are missing or partially missing, AEs will be assumed to be treatment-emergent. Handling of missing dates/times for classification of AEs as TEAEs is described in [Section 4.2.7](#).

The following rules will be used to assign a TEAE to a study period:

- A TEAE will be assigned to the Dosing Period for the tabulations if the start date/time of the event is at the time of or after the first administration of UCB7665 until 7 days after the final dose; for the purpose of the analysis this will be calculated as the start date/time of the final infusion plus 168 hours;
- A TEAE will be assigned to the Observation Period for the tabulations if the start date/time of the event is greater than 7 days after the final dose until 8 weeks following the final dose; events starting later than 8 weeks following the final dose of UCB7665 are not considered as TEAEs.

Adverse events with missing start date/times will be handled as described in [Section 4.2.7](#) for this classification.

The number and percentage of subjects who experience TEAEs will be summarized for each dose arm and overall. The following summaries will be presented:

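### Log-rank test, total AUEC and TEAE percentages can differ between arms through visit timing and follow-up length alone

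*SAP*

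**What the plan says.** **AUEC.** SAP Section 8.1.1 asks for "Baseline-corrected AUEC for platelet count calculated from Baseline to the end of study visit for each of the defined dose arms", by the linear trapezoidal rule, as a total in 10^9/L*day. Section 2.2.2 sets where it stops. Arm 1 ends at Day 85 and Arm 2 at Day 71, and for the remaining arms the text reads "Day 64 in the Observation Period in Dose Arm 3 and Day 57 in Observation Period in Dose Arms 4 and 5". There is no common cut-off. Section 8.1.1 sets minimum numbers of counts: 10 of 14 in Arm 1, 9 of 12 in Arm 2, 8 of 11 in Arm 3, and "a minimum of 7 out of 9 must be available for the calculation in Dose Arms 4 and 5". It adds: "The AUEC will not be calculated in the case of early withdrawal from the study".

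**Visits.** In Section 3.2.1.2 the Observation Period is tied to the last dose: "a visit will be scheduled 3 days after the final dose (or only dose administration for Dose Arms 4 and 5) and weekly thereafter", for 8 weeks.

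**Time to response.** Section 8.1.3.2 plans Kaplan-Meier curves and reports "the p-value for the log-rank test for the equality over dose arms". Non-responders are censored at end of study or withdrawal.

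**TEAEs.** In Section 10.2 events count up to 8 weeks after the final dose. The Dosing Period table covers events starting "at the time of or after the first administration of UCB7665 until 7 days after the final dose". Tables give subject counts, percentages and event counts, with no rate per unit of time.

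**The concern.** All three displays put the five regimens side by side, but the arms are not observed alike. A response can be seen only when a count is taken, and Arms 4 and 5 are scheduled for a count earlier than the others. A total area grows with the time over which it is taken. A crude percentage of subjects with an event grows with the time at risk. The number of doses sets all three, so schedule and regimen are confounded.

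At stake is a misreading of the regimens. Single-dose arms could appear to act faster, Arm 1 could appear to have more total platelet effect, and Arm 1 could appear less well tolerated on the primary safety variable. The SAP gives no caution and no sensitivity analysis for this.

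**Working it through.** **Windows and visits.** Doses are weekly from Day 1, so the last dose falls on Day 29, 15, 8 or 1. Adding 56 days gives Day 85, 71, 64 and 57, which reproduces Section 2.2.2 exactly. Measured from Day 1 the windows are 84, 70, 63 and 56 days. The Dosing Period windows (last dose + 7 days, from Day 1) are 35, 21, 14 and 7 days. The visit 3 days after the last dose falls on Day 32, 18, 11 or 4. The ADA schedule in Section 2.2.4 lists the same four days.

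**(a) Log-rank test.** The first scheduled post-dose visit is Day 4 in Arms 4 and 5 and Day 8 in Arms 1 to 3. I simulated identical onset in all arms, detected at the next scheduled visit, with n = 15/15/12/12/12 (or 6 in each of Arms 3 to 5), 70% responding, and a 4-df chi-square test at 5%. The ranges cover repeat runs and both arm sizes.

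| Onset, same in every arm | Rejection, planned visits | Rejection, common weekly visits |
|---|---|---|
| All responders by Day 4 | 66 to 70% | 4 to 5% |
| Uniform, Days 2 to 8 | 15 to 23% | 3 to 6% |
| Uniform, Days 2 to 15 | 7 to 8% | 5 to 6% |
| Uniform, Days 2 to 22 | 6 to 7% | about 6% |

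Exponential onset with every subject eventually responding behaves the same way. A 3-day median gives 53% on planned visits and 5% on common visits. A 7-day median gives 10 to 14% on planned visits. A median of 14 days or more gives 6 to 10%, about the level with equal windows.

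To isolate follow-up length, I treated onset as observed exactly. For medians of 3, 14 and 40 days, rejection was 8.1, 7.1 and 6.2% with unequal windows and 8.4, 7.6 and 5.8% with equal ones. Length therefore adds nothing. Cutting all arms at Day 57 but keeping the planned visits left 52%, so the visit days are the cause.

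**(b) AUEC.** Trapezoid on each arm's scheduled days, with the same curve in every arm (Arms 1 / 2 / 3 / 4 and 5):

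- Constant effect: ratios to Arms 4 and 5 are 84/56 = 1.50, 70/56 = 1.25 and 63/56 = 1.125.
- Rise to +50 over 7 days, then flat: ½×7×50 + 50×(window − 7) = 4025 / 3325 / 2975 / 2625.
- Peak of 75 at 7 days, linear decline to zero at 84 days: 3150 / 3055 / 2935 / 2768, so Arm 1 is 14% higher.
- Peak of 75 at 7 days, gone at 28 days: ½×28×75 = 1050 in every arm. Gone at 49 days: 1838 in every arm.
- Peak of 75 at 4 days, gone at 28 days: 919 / 919 / 919 / 1017. The Day 4 count captures more of the peak, so Arms 4 and 5 come out 11% higher.

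**(c) TEAEs.** With a constant hazard giving incidence p in 56 days, incidence in w days is 1 − (1 − p)^(w/56).

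| | Arm 1 | Arm 2 | Arm 3 | Arms 4, 5 |
|---|---|---|---|---|
| p = 25%, whole study | 35.0% | 30.2% | 27.6% | 25.0% |
| p = 50%, whole study | 64.6% | 58.0% | 54.1% | 50.0% |
| p = 50%, Dosing Period | 35.2% | 22.9% | 15.9% | 8.3% |

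**(d) Planned counts.** Dosing visits + the 3-day visit + 8 weekly visits give 5+1+8 = 14, 3+1+8 = 12, 2+1+8 = 11 and 1+1+8 = 10. Section 8.1.1 agrees for Arms 1 to 3 but states 9 for Arms 4 and 5.

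**The case against.** The strongest reply is that nothing is decided on these displays. The main efficacy variable is maximum increase, tested within arm (Section 8.1.3.1). AUEC is one of twelve summarised items with no between-arm test, TEAEs are not tested, and Section 8.1.3.2 places the log-rank p-value among descriptive statistics. Dose-arm openings rest on interim safety data under a separate SAP (Section 4.4). This stands. A reader might infer that dose selection hangs on these tables, and the SAP does not say so.

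Two other stronger readings also fail. One is that unequal follow-up biases the log-rank test. It does not, because censoring handles it, as the check in (a) shows. The other is that arms with equal effect will always look different. AUEC depends on the window only if the effect outlasts Day 57, and log-rank inflation needs many first-week responses. The SAP gives no onset time or duration of effect.

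Following every arm for 8 weeks after its last dose is a reasonable design, and total AUEC does describe each regimen's full course. That justifies keeping it, but not using it alone to compare arms. On TEAEs, event counts accompany the percentages and listings show days since dosing. These help, but they give no comparable rate.

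Unscheduled counts may enter time to response (Section 8.1.1), and the simulation omits them. Finally, 9 would be right if no platelet count is taken on Day 4, and limb (a) would then fall away. The match in Arms 1 to 3 makes a slip more likely, but the platelet schedule itself has to settle it.

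**Conclusion.** The concern holds as a comparability problem of moderate weight: these displays can differ between arms with equal drug effect. The log-rank test is the most exposed, because it is the only one of the three with a planned between-arm test. Its illustrative rejection under equal effect is about 15 to 25% for onset spread over week 1, about 70% if all responders respond by Day 4, and near nominal for onset spread over two weeks or more. Total AUEC can differ up to about 1.5-fold for a sustained effect and is essentially unaffected by the window for one gone by Day 57. TEAE percentages differ whenever events continue through follow-up, most of all in the Dosing Period table, where windows differ five-fold (35 against 7 days).

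Onset times, the 70% response proportion (a higher one raises the rejection rate), curve shapes and constant hazards are my assumptions. The windows and visit days come from the SAP. The mismatch of 9 and 10 is a separate, minor inconsistency.

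**What to change.** 1. **Log-rank test:** use only visits common to all arms (Days 8, 15, 22, 29, 36, 43, 50, 57), or an interval-censored method on all counts. With common visits, off-week counts are lost to this test only.
2. **AUEC:** add AUEC from Baseline to Day 57 in all arms as the comparable summary and keep the per-arm total as secondary. By the visit rule each arm has 10 scheduled counts to Day 57 (14−4, 12−2, 11−1, 10), so one completeness rule can serve all arms. Using weekly visits only would also remove the small Day 4 effect. Do not divide AUEC by each arm's own or observed days. For the effect gone at 28 days, 1050 divided by 84, 70, 63 and 56 gives 12.5, 15.0, 16.7 and 18.8, a false 1.5-fold difference the other way.
3. **TEAEs:** add incidence in the first 56 days after first dose, and events per subject-time by period.
4. **Counts:** check 9 against the platelet schedule for Arms 4 and 5 and correct whichever statement is wrong.

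The cost is SAP wording and a few extra tables. No new data are needed.
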